7.3 Definition of Unanticipated Adverse Device Effect (UADE)

Any serious adverse effect on health or safety or any life-threatening problem or death caused by, or associated with, a device, if that effect, problem, or death was not previously identified in nature, severity, or degree of incidence in the investigational plan or application (including a supplementary plan or application), or any other unanticipated serious problem associated with a device that relates to the rights, safety, or welfare of subjects.

7.4 Severity of Adverse Device Event

• Mild (1 = Grade 1): Awareness of signs or symptoms, but easily tolerated; are of minor irritant type, causing no loss of time from normal activities; symptoms would not require medication or a medical evaluation; signs and symptoms are transient.

- Moderate (2 = Grade 2): Discomfort severe enough to cause interference with usual activities; requiring treatment but not extended hospitalization or intensive care for the subject.
- Severe (3 = Grade 3): Incapacitating with inability to do work or usual activities; signs and symptoms may be systemic in nature or require medical evaluation and/or treatment; requiring additional hospitalization or intensive care (prolonged hospitalization).
- Life-threatening (4 = Grade 4): At immediate risk of death in view of the investigator, or it is suspected that the use or continued use of the product would result in subject's death; urgent intervention indicated.
- **Death (5 = Grade 5):** Death related to adverse event.

7.5 Relatedness of ADE and SADE

- Unrelated: This category applies to those adverse events which, after careful consideration, are clearly and incontrovertibly due to extraneous causes (disease, environment, etc.)
- **Possible:** This category applies to those adverse events for which, after careful medical consideration at the time they are evaluated, a connection with the Investigational Product administration appears unlikely but cannot be ruled out with certainty.
- **Probable:** This category applies to those adverse events which, after careful medical consideration at the time they are evaluated, are felt with a high degree of certainty to be related to the Investigational Product.
- **Definite:** This category applies to those adverse events which, after careful consideration, are clearly and incontrovertibly due to the Investigational Product.

7.6 Expectedness

The site PI will be responsible for determining whether an ADE or SADE is expected or unexpected. An ADE will be considered unexpected if the nature, severity, or frequency of the event is not consistent with the risk information previously described for the medical device.

Expected ADEs include a reaction or irritation at the study site following application of the sensors or the site from where blood is drawn.

7.7 Adverse Device Event Reporting

The ADEs will be recorded on the Adverse Event form, provided by Medline Industries, LP, by the site PI. Changes in the severity of an ADE will be documented to allow an assessment of the duration of the event at each level of severity. Changes in severity will necessitate a new CRF to document the new level of severity. ADEs characterized as intermittent require documentation of onset and duration of each episode.

Non-serious ADEs are to be reported to the study sponsor for review and reported to the IRB per IRB reporting requirements.

7.8 Serious Adverse Device Event and Unanticipated Adverse Device Effect Reporting

The site PI shall complete a SAE Form provided by Medline Industries, LP and submit to the study sponsor, but in no event later than 48 hours after the investigator first learns of the effect. The site PI shall report the SADE to the reviewing IRB, if applicable, according to their reporting requirements. The study sponsor is responsible for conducting an evaluation of the SADE and shall report the results of such evaluation to the FDA and to all reviewing IRBs if applicable within 10 working days after the sponsor first receives notice of the effect. Thereafter, the sponsor shall submit such additional reports concerning the effect as FDA requests.

For questions regarding this process or the event, you may contact your Medline clinical designee or the Medline Director of Clinical Operations:

Name: [name] RN, BSN, CCRA [contact] E-mail: [contact]

8 STATISTICAL CONSIDERATIONS

8.1 Sample Size Determination

Data from a study assessing the accuracy of both pulse oximeters on an adult population (Study ID # 2018-268) were used as parameters for sample size estimation for this protocol. Sample size estimation was conducted separately for each product using both the Confidence Intervals for One Standard Deviation Using Standard Deviation (as an estimate for the accuracy root mean square A_{RMS} statistic in equation 1.1 below) and Bland-Altman procedures in PASS 2020 Power Analysis and Sample Size Software (2020). NCSS, LLC. Kaysville, Utah, USA, ncss.com/software/pass. The most conservative estimate between the two products for the A_{RMS} sample size (18) and the Bland-Altman statistic (40) was used as the minimum number of data pairs, n. A data pair will consist of a pulse oximeter sensor reading paired with an ABG reading collected by a CO-oximeter. We selected a sample size of at least 80 total data pairs for each of the two product sensors, consisting of at least 40 data pairs per site per product sensor. We doubled this estimate and selected a sample size of at least 80 total data pairs per product sensor, such that no subject contributes more than three data pairs for each of the two product sensors, for a minimum of 27 subjects. The same blood gas value can be used for multiple sensors applied simultaneously.

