|-----------------------------------------------------------|------------------------------------------------------------------------------------------------------------------------------------------------------------------------------------------------------------------------------------------------------------------------------------------------------------------------------------------------------------------------------------------------------------------------------------------------------------------------------------------------------------------------------------------------------------------------------------------------------------------------------------------------------------------------------|
| | Inclusion Criteria Subjects who are postnatal 28 days or younger (neonates) Subjects who are likely to receive one or more ABG measurements as part of their clinical SOC. Subjects who weigh less than 5 Kg (weight range for the sensors) |
| | Exclusion Criteria Subjects with current signs and symptoms of a clinically significant Patent Ductus Arteriosus (PDA) combined with a current or planned arterial line placement which will affect the validity of the co-oximetry measurement Subjects with physical malformation of hands, fingers, feet, or toes that would limit the ability to place sensors for this study Subjects judged by the Principal Investigator (PI) to be inappropriate for participation in this study Subjects for whom placing a pulse oximeter will cause dermatological issues (e.g. allergic to foam rubber or adhesive tape) |
| Phase: | Post-Market |
| Description of Sites/Facilities Enrolling subjects: | Multiple neonatal intensive care centers |
| Description of Study: | Data collection will take place at the sites. The PI or designee will place one or both of the pulse oximeter sensors (Medline ReNewal [™] Reprocessed Masimo LNCS Series SpO2 Adhesive Sensors, Neo (2329) and Medline Renewal [™] Reprocessed Nellcor [™] OxiMax SpO2 Sensor, MAXN) on hands and/or feet of the subjects according to the IFU and record the readings. The arterial blood sample used in this study will be taken in the normal course of care and will be measured in the reference CO-oximeter |

Accuracy of SpO₂ of reprocessed pulse oximetry sensors compared to SaO₂ assessed by CO-oximetry in neonates MED-2020-DIV65-001 May 9, 2022 V 3.0

for SaO₂. This arterial sample will be obtained from a systemic artery.

Anticipated Six months to one year **Enrollment period:**

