8.4 Data Analysis

Accuracy of each pulse oximeter will be assessed per ISO 80601-2-61:2017, the FDA "Pulse Oximeters - Premarket Notification Submissions [510(k)s] Guidance for Industry and Food and Drug Administration Staff" document issued on March 4, 2013, and paper by Bland et al., 2007.^{3,4,5}

For each pulse oximeter, an accuracy root mean square (A_{RMS} , in equation 1.1 below) will be calculated to define the SpO₂ accuracy compared to the SaO₂ as measured by co-oximeter, as outlined in ISO 80601-2-61:2017 sub clause 201.12.1.101. It is expected that each of the sensors should achieve an $A_{RMS} \leq 3\%$ as per the testing of these same products in the protocol on adult subjects. In addition, mean Bias (B, in equation 1.2) defined per ISO 80601-2-61:2017 as the mean difference between the test and reference values, preserving sign, and precision (SD_{res} , in equation 1.3), defined per ISO 80601-2-61:2017 as the standard deviation of the residuals.

In the following equations, let

- SpO_{2_i} be the oxygen saturation value for the i^{th} data pair in the range of interest measured using the pulse oximeter
- SaO_{2i} be the reference oxygen saturation value for the *i*th data pair in the range of interest measured using the co-oximeter
- and *n* be the number of data pairs in the sample in the range of interest.

Then, per ISO 80601-2-61:2017 A_{RMS} is defined as:

$$A_{RMS} = \sqrt{\frac{\sum_{i=1}^{n} (SpO_{2_i} - SaO_{2_i})^2}{n}}$$
(1.1)

Mean bias B is defined as:

$$B = \frac{\sum_{i=1}^{n} (SpO_{2_i} - SaO_{2_i})}{n}$$
(1.2)

And precision (SD_{res}) is defined as:

$$SD_{res} = \sqrt{\frac{\sum_{i=1}^{n} (SpO_{2_i} - SpO_{2fit_i})^2}{n-2}}$$
(1.3)

where SpO_{2fit_i} is the difference between the *i*th datum and the value of the fitted curve corresponding to the *i*th reference value

For each pulse oximeter, a Bland-Altman plot (mean vs. difference of SaO_2 and SpO_2) and an error plot (SaO_2 vs. difference of SaO_2 and SpO_2) will be generated. Between and within subject variance and upper and lower 95% limits of agreement will be presented. Subject demographic data will be presented with summary statistics and site-level effects will be assessed as appropriate. Outliers will be explained and any data that is excluded from the data analysis or any deviations from this statistical analysis plan will be justified in the final report.

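### Section 8.1 sizes the trial in pairs with no stated allowance for up to three pairs per infant, its 27-infant minimum contradicts its 40-per-site rule, and 8.4 plans no interval at infant level

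*Combined protocol and SAP*

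**What the plan says.** Section 8.1 runs two sizing procedures, a confidence interval for one standard deviation (standing in for A_RMS) and a Bland-Altman calculation. The larger result becomes the floor: the A_RMS "sample size (18) and the Bland-Altman statistic (40) was used as the minimum number of data pairs, n". The unit is the reading, not the infant: "A data pair will consist of a pulse oximeter sensor reading paired with an ABG reading collected by a CO-oximeter".

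The section then reaches 80 pairs per sensor in two consecutive sentences. The first describes the 80 as "consisting of at least 40 data pairs per site per product sensor". The second says "We doubled this estimate and selected a sample size of at least 80 total data pairs per product sensor", and adds the cap and the infant count: "such that no subject contributes more than three data pairs for each of the two product sensors, for a minimum of 27 subjects". The number of sites is not given; the synopsis (1.1) says only "Multiple neonatal intensive care centers".

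The sizing inputs are attributed to "Data from a study assessing the accuracy of both pulse oximeters on an adult population", but no SD, mean difference, agreement limit, interval width, alpha or power is printed.

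Section 8.4 gives A_RMS, bias and precision as formulas over pairs. It also promises: "Between and within subject variance and upper and lower 95% limits of agreement will be presented". It plans no confidence interval or test for A_RMS, bias or the limits. The expectation that A_RMS is at most 3% is therefore read off a point estimate.

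**The concern.** Up to three pairs come from one infant, and section 6.2.6 allows the same sensor to be used for all three. Errors within an infant may therefore be correlated, and 80 pairs may carry less information than 80 independent readings. Section 8.1 neither mentions this nor offers the doubling as a remedy for it. The per-site sentence also gives the same 80 a different purpose.

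Two things are at stake. A site lead or monitor cannot tell whether recruitment is complete at 80 pairs pooled or at 40 pairs in each site, and the printed infant minimum fits only the first. And a reader of the final report will see an A_RMS from possibly 27 infants with no statement of its uncertainty, although one of the two sizing procedures was itself an interval calculation.

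**Working it through.** **1. The plan's own figures.** 2 × max(18, 40) = 80, and 80/3 = 26.7, rounded up to 27. Both reproduce. The 18 and 40 cannot be checked because their inputs are not printed.

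**2. The 27 against the per-site rule.** With at most three pairs per infant per sensor, 13 infants give at most 39 pairs, so 40 pairs need 14 infants.
- Two sites: 14 + 14 = 28 infants. With 27 infants, one site has at most 13 and so at most 39 pairs.
- Three sites: 3 × 14 = 42 infants and 3 × 40 = 120 pairs, which is no longer a total of 80.

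This step needs no assumption about correlation.

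**3. Effective pairs.** Assume normal errors, three pairs per infant and a common within-infant correlation r. The documents give no r, so a range is shown. The design effects are:
- mean bias: 1 + 2r
- SD, and approximately A_RMS when bias is small: 1 + 2r²
- a limit of agreement (mean ± 1.96 SD): [(1 + 2r) + 1.92(1 + 2r²)] / 2.92, where 1.92 = 1.96²/2

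Effective pairs are the actual pairs divided by the design effect. For example, bias at r = 0.3 gives 80/1.6 = 50.

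| r | Bias, of 80 | Limit, of 80 | A_RMS, of 80 | Limit, of 40 |
|---|---|---|---|---|
| 0.1 | 67 | 74 | 78 | 37 |
| 0.3 | 50 | 60 | 68 | 30 |
| 0.5 | 40 | 48 | 53 | 24 |
| 0.7 | 33 | 38 | 40 | 19 |
| 0.9 | 29 | 30 | 31 | 15 |

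**4. Where the pooled 80 falls below 40.**
- Bias: 1 + 2r = 2, so r = 0.50.
- Limit of agreement: 3.84r² + 2r − 2.92 = 0, so r ≈ 0.65.
- A_RMS is compared with its own minimum of 18. The worst case, r = 1, gives 80/3 = 26.7, so 18 is always met.

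If 40 is instead a target for each site, any r above 0 puts the site below it when infants give three pairs each. At r = 0.2 the site has 40/1.4 = 28.6 effective pairs for bias and 33.6 for a limit.

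**5. What an interval computed on pairs would do.** For bias, the true standard error is √(1 + 2r) times the pair-level one. Coverage of a nominal 95% interval is therefore about 2Φ(1.96/√(1 + 2r)) − 1, which is 93%, 88%, 83%, 79% and 76% at r = 0.1, 0.3, 0.5, 0.7 and 0.9. Simulation of 20,000 trials with 27 infants × 3 pairs agrees within about one point. A t-interval on the 27 infant means held 95% throughout.

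**The case against.** The strongest reply is that the plan asks for 40 and collects 80. That stands for the pooled reading. A reader might infer that clustering leaves the trial short of its own requirement, but the documents do not support this. The 40 is a floor rather than the planned information, and the pooled 80 keeps 40 effective pairs up to quite high correlations. The 40 also comes from the Bland-Altman procedure, so its natural threshold is the limit-of-agreement one, about 0.65; bias has no sizing target of its own.

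A reader might also infer that the plan reports intervals that are too narrow. It does not, because no interval is planned. The coverage figures describe what would happen if one were added and computed on pairs. Nor did the authors overlook repeated readings. Section 8.4 cites a methods paper on multiple observations per individual for the assessment of accuracy as a whole, and it commits to splitting between- from within-subject variance. What it leaves out is how those components enter the limits of agreement.

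Three further points have weight. Three pairs is a cap and 27 and 80 are floors, so infants giving one or two pairs would soften the clustering and raise the infant count. Nothing says each site must reach the precision target alone. And the effect on the 3% expectation may be small: in a simulation with an assumed SD of 2, even at ICC 0.9, the point estimate passed in essentially every trial and a pair-level one-sided upper bound stayed at or below 3 in 99%. An SD nearer 3 would be more sensitive.

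None of this reconciles 27 infants with at least 40 pairs per site, or supplies the missing intervals.

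**Conclusion.** The point holds in a limited form. As written, the minimum of 27 infants cannot satisfy the per-site rule in a multi-site trial; the rule needs 28 infants for two sites and 42 for three. That finding rests only on the cap of three pairs. The two accounts of 80 are not reconciled, and neither is stated to be an allowance for clustering.

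A loss of information below the calculated 40 is conditional. Pooled, it requires an ICC above 0.50 (bias) or about 0.65 (limits of agreement). Per site, any positive ICC is enough. Both statements assume three pairs per infant and exchangeable normal errors, and the documents give no ICC with which to choose between the cases. They do not show that the trial is too small, nor that its conclusion on A_RMS would change.

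The analysis gap is the absence of any interval for A_RMS, bias or the limits, and of any rule that a later interval must treat the infant as the sampling unit.

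**What to change.** **Section 8.1.** State whether the target is 80 pairs pooled or 40 per site, give one reason for the 80, and name the number of sites. Match the infant minimum to the choice: 27 only if pooled, 28 if 40 per site with two sites. Print the inputs behind 18 and 40, and the effective pairs over a stated ICC range.

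**Section 8.4.** Report 95% intervals for A_RMS, bias and both limits of agreement with the infant as the unit, either by resampling infants (cluster bootstrap) or from the variance components already planned. Say explicitly that the limits of agreement are built from those components.

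**Cost.** A wording change and a short extra step in the SAS analysis. Under the two-site reading the infant minimum rises by one; with more sites, keeping the per-site rule would raise the pair total as well. The reported intervals will be wider than pair-level ones would be.

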8.2 Randomization

Randomization will not be completed as the data are collected from a convenience sample of subjects.

8.3. Populations for Analysis

All data pairs will be included for analysis, unless at the time of data acquisition any one or more of the following is true: (1) the SpO2 value is >100%; OR (2) the SpO2 value is \leq 0%; OR (3) the heart rate measurement derived from the pulse oximeter is 0 beats per minute; OR (4) the research personnel collecting the data notes an anomaly in the measurement on the CRF at the time of data collection before data analysis begins. Any such designated outliers and/or anomalous data will be explained and any data that is excluded from the analysis will be justified in the final report.

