5. STUDY POPULATION

5.1. Inclusion Criteria

Subjects, who satisfy *ALL* of the inclusion criteria below, will be eligible to participate in the study:

- Subjects who are postnatal 28 days or younger (neonates).
- Subjects who are likely to receive one or more arterial blood gas measurements as part of their clinical standard of care
- Subjects who weigh less than 5 Kg (weight range for the sensors).

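### With SpO2 bounded at 100% and no SaO2 limit or coverage set, a highly saturated sample lets a sensor whose error exceeds 3% at lower saturations meet the 3% A_RMS expectation

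*Combined protocol and SAP*

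**What the plan says.** Section 8.3 keeps every pair unless one of four conditions holds. The first is "any one or more of the following is true: (1) the SpO2 value is >100" per cent; the others are SpO2 at or below zero, a heart rate of zero, and an anomaly noted at collection. None depends on SaO2, and a reading of exactly 100% stays in.

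Section 8.4 computes one A_RMS (equation 1.1), one mean bias B (1.2) and one precision figure (1.3) per sensor. The pair count n is said to "be the number of data pairs in the sample in the range of interest", but no limits for that range appear anywhere. On acceptance, the section says "It is expected that each of the sensors should achieve an" A_RMS of at most 3%, with reference to the adult study. It also plans a Bland-Altman plot, an error plot against SaO2 and 95% limits of agreement.

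Section 8.2 says that "the data are collected from a convenience sample of subjects". The only eligibility condition touching blood gases (5.1) is "Subjects who are likely to receive one or more arterial blood gas measurements as part of their clinical standard of care"; no saturation level or spread is required. Both sets of instructions for use (IFUs) in the appendix give an SpO2 range of 70–100%.

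**The concern.** No analysed SpO2 exceeds 100%, so the largest positive difference that can enter equations 1.1 and 1.2 is 100 − SaO2. Above SaO2 97%, a +3-point error cannot appear at all. Large positive errors are lost near the top of the scale; negative errors are not.

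The plan does not control how many pairs lie near the top. If most do, the pooled A_RMS falls for a reason unrelated to how the sensor behaves at 85% or 75%. A result of 3% or less could then be read as support for the whole 70–100% range when it says little about the lower part. The adult tables show that error can differ by band: A_RMS for Neo 2329 was 0.9 at 90–100% and 2.1 at 70–80%; for MAXN it was 1.5 and 2.1. The neonatal plan has no such breakdown.

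**Working it through.** **Plan's own figures.** 2 × 40 = 80 pairs per sensor; 80 / 3 = 26.7, so 27 infants. Both reproduce. The components 18 and 40 cannot be checked, because confidence level, interval width, agreement limit and power are not stated. The 80 pairs are used below.

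**Model (assumed).** Recorded error d = min(e, c), with c = 100 − SaO2 and e normal with mean b and SD s. The uncapped A_RMS is √(b² + s²). With z = (c − b)/s:

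- E[d²] = (b² + s²)Φ(z) − s(b + c)φ(z) + c²(1 − Φ(z))
- E[d] = bΦ(z) − sφ(z) + c(1 − Φ(z))

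Example: b = 3, s = 2, SaO2 97, so c = 3 and z = 0. E[d²] = 13 × 0.5 − 2 × 6 × 0.399 + 9 × 0.5 = 6.21, and A_RMS = 2.49. E[d] = 1.5 − 0.80 + 1.5 = 2.20.

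**All pairs at one SaO2 value (expected A_RMS; mean error):**

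| SaO2 | b = 0, s = 3.5 (uncapped 3.50) | b = +3, s = 2 (uncapped 3.61) |
|---|---|---|
| 90 | 3.49; 0.00 | 3.61; +3.00 |
| 94 | 3.37; −0.06 | 3.49; +2.94 |
| 95 | 3.27; −0.12 | 3.32; +2.83 |
| 97 | 2.95; −0.38 | 2.49; +2.20 |
| 98 | 2.75; −0.62 | 1.80; +1.60 |
| 99 | 2.56; −0.95 | 0.98; +0.83 |

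At SaO2 100 the zero-bias value is s/√2, so an SD up to 3 × √2 = 4.24 still gives 3% or less.

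**Chance of A_RMS ≤ 3%, 80 independent pairs, SaO2 uniform (simulated, 20,000 repeats):**

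| SaO2 mix | b = 0, s = 3.5 | b = +3, s = 2 |
|---|---|---|
| no ceiling | 3.6% | 0.2% |
| 70–100 | 8% | 3% |
| 90–100 | 29% | 59% |
| 94–100 | 61% | over 99% |

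The 3.6% is chance alone: P(χ² on 80 df ≤ 80 × 9 / 12.25 = 58.8).

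**Sensitivity.**
- Dropping readings above 100% instead of capping them: the zero-bias SD 3.5 sensor at 94–100 passes 44% of the time instead of 61%.
- Within-subject correlation 0.5: a zero-bias sensor with SD 4.0 at 94–100 passes 23% instead of 17%.
- Under-reading sensor (uncapped 3.5, bias −2) at 94–100: 5.5%, against 2.9% with no ceiling.

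**Where to place an SaO2 limit (zero bias, SD 3.5, 80 pairs).** With SaO2 uniform on 85–94, A_RMS is 3.48 and the pass rate 4%, close to the no-ceiling result. On 90–97 it is 3.34 and 9%.

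**The case against.** **The documents do not say that the display stops at 100%.** True; section 8.3 only excludes higher values. Capping and exclusion both remove the largest positive errors, though, so the point does not depend on which happens. Deleting the exclusion alone would not help if the monitor caps.

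**The recorded error near 100% is the error the clinician sees.** This stands. It is tempting to infer that the plan hides hypoxia in the infants sampled, or that their recorded errors are wrong. The documents do not support that: clipping acts mainly at SaO2 of about 95% and above. The fault is only in carrying the result to lower saturations.

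**Planned outputs would show the pattern.** Partly true. The error plot would show the SaO2 mix and an upper edge at 100 − SaO2, and the over-reading sensor would still report bias of +2.2 at SaO2 97 and +1.6 at 98. But none of these outputs changes the 3% comparison, and B and the limits of agreement use the same clipped differences.

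**The sizes are hypothetical.** True. The SaO2 mix is unknown, and an error of 3.5 is about twice the adult 70–100% values (3.5/1.6 = 2.2; 3.5/1.7 = 2.1).

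**The 3% figure is an expectation with no stated hypothesis test.** Also true. It is still the only accuracy benchmark in the plan, and a report will be read against it.

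**Conclusion.** The point holds in a conditional form. With no limits on the range of interest and no required saturation spread, a sample mostly at SaO2 of about 95% or more can let an unbiased or over-reading sensor meet 3% when its error at lower saturations is larger. For a zero-bias sensor with SD 3.5, the chance rises from about 4% with no ceiling to 8%, 29% and 61% as the SaO2 mix moves from 70–100 to 90–100 to 94–100. For a +3-point sensor with SD 2, it is 59% and over 99% in the last two mixes. These figures rest on normal errors, independent pairs and uniform SaO2, none of which the documents supply.

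A reader might infer that a poor sensor will pass this study. The documents do not support that: the effect is small if most pairs lie below about 92%, and an under-reading sensor gains little. A reader might also take SaO2 ≤ 97% as a complete cure, because a +3-point error can just be displayed there. It only reduces the clipping: at exactly 97% the two example sensors still show 2.95 and 2.49.

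**What to change.** In section 8.4, before analysis:

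- Define the range of interest by SaO2. Never select by SpO2, which contains the error being measured.
- Beside the all-pairs figures, report A_RMS and B for pairs below a pre-set SaO2 limit, with the number of pairs and a confidence interval that allows for repeated pairs per infant. A limit of about 94–95% nearly removes the clipping.
- Report the SaO2 distribution and the number of SpO2 readings equal to 100%, per sensor.
- State that the 3% conclusion applies only to the SaO2 range observed, and is not extended to lower saturations if the subset has few pairs or its A_RMS exceeds 3%.

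Do not make the subset a hard pass condition. Small subsets pass by chance: with no ceiling, an SD 3.5 sensor gives A_RMS ≤ 3% about 31% of the time with 10 pairs and 21% with 20, against 3.6% with 80.

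The cost is SAP wording and one table row per sensor. That row has fewer pairs and is less precise: with SaO2 uniform on 90–100, a limit of 94% leaves about 80 × 4/10 = 32 pairs; on 94–100, a limit of 95% leaves about 80 × 1/6 = 13.
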